5.7.2.1 Dose delay criteria for IMP

Dose delay criteria apply for all drug-related AE. A treatment delay up to 4 weeks, *i.e.*, ≤6 weeks calculated from start of the previous therapy cycle, is allowed. A treatment delay beyond 6 weeks is not allowed ([Paragraph 5.7.2.3](#)).

Tumor assessments should continue as per protocol schedule, even if dosing is delayed.

Nivolumab administration will be delayed for the following reasons (in CTCAE grading):

- Any grade ≥2 non-skin drug-related AE, except for fatigue and laboratory abnormalities.
- Any grade 3 skin drug-related AE.
- Any grade 3 drug-related laboratory abnormality.
- Any AE, laboratory abnormality, intercurrent illness, or other reason which, in the judgment of Clinical Investigator, warrants delaying the dose of study medication.

Subjects who require delay of nivolumab will be re-evaluated weekly, or more frequently if clinically indicated. Nivolumab dosing can be resumed on the established dosing schedule when retreatment criteria are met ([Paragraph 5.7.2.2](#)).

FLOX administration will be delayed for the following reasons (in CTCAE grading):

- Grade 2 diarrhea (increase of 4–6 stools per day over baseline; moderate increase in stoma output compared to baseline; not interfering with ADL).
- Grade 3 diarrhea (increase of 7 or more stools per day over baseline; incontinence; severe increase in stoma output compared to baseline; interfering with ADL).
- Grade 2 myelosuppression (neutrophils of $1.0 \times 10^9/L$ to less than $1.5 \times 10^9/L$, or platelets of $50 \times 10^9/L$ to less than $75 \times 10^9/L$).
- Grade 3 myelosuppression (neutrophils of $0.5 \times 10^9/L$ to less than $1.0 \times 10^9/L$, or platelets of $25 \times 10^9/L$ to less than $50 \times 10^9/L$).
- Grade 4 myelosuppression (neutrophils less than $0.5 \times 10^9/L$, or platelets less than $25 \times 10^9/L$).
- Grade 2 sensory neuropathy (sensory alteration or paresthesia persisting between two oxaliplatin doses with no or only minor improvement, moderate symptoms, limiting instrumental ADL).

Subjects who require delay of FLOX will be re-evaluated weekly, or more frequently if clinically indicated. FLOX administration will be resumed when retreatment criteria are met ([Paragraph 5.7.2.2](#)).

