5.7.2.2 Criteria to resume dosing for IMP

Subjects may resume treatment with study drug when the drug-related AE resolves to CTCAE grade ≤ 1 or baseline value, with the following exceptions:

For nivolumab:

- Subjects may resume nivolumab treatment in accordance with the below criteria irrespective of whether FLOX or nivolumab was administered in the preceding cycle.
- Subjects may resume treatment in the presence of CTCAE grade 2 fatigue.
- Drug-related pulmonary toxicity, diarrhea, or colitis must have resolved to baseline before treatment is resumed.
- Subjects with drug-related endocrinopathies adequately controlled with only physiologic hormone replacement may resume treatment.
- Subjects who received systemic corticosteroids for management of any drug-related toxicity must be off corticosteroids or have tapered down to an equivalent dose of prednisolone ≤ 10 mg/day.

For FLOX:

- Subjects may resume FLOX treatment in accordance with the below criteria (in CTCAE grading) irrespective of whether FLOX or nivolumab was administered in the preceding cycle.
- Grade 2 diarrhea; the following pertaining to both oxaliplatin and fluorouracil: interrupt until grade 1 or less, then 100% dose first time, 75% dose second time, 50% dose third time.
- Grade 3 diarrhea; the following pertaining to both oxaliplatin and fluorouracil: interrupt until grade 1 or less, then 75% dose first time, 50% dose second time, discontinue third time.
- Grade 2 myelosuppression; the following pertaining to both oxaliplatin and fluorouracil: interrupt until grade 1, then 100% dose first time, 75% dose and consider support with granulocyte-colony stimulating factor (e.g., pegfilgrastim) second or subsequent times.
- Grade 3 myelosuppression; the following pertaining to both oxaliplatin and fluorouracil: interrupt until grade 1 or less, then 75% dose and consider support with granulocyte-colony stimulating factor (e.g., pegfilgrastim) first or subsequent times.
- Grade 4 myelosuppression; the following pertaining to both oxaliplatin and fluorouracil: interrupt until grade 1 or less, then 50% dose and consider support with granulocyte-colony stimulating factor (e.g., pegfilgrastim) first or subsequent times.
- Grade 2 sensory neuropathy; the following pertaining only to oxaliplatin: interrupt until grade 1 or less, then 75% dose first time, 50% dose second time, discontinue third time.

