- Any event that leads to delay in dosing lasting >6 weeks from start of the previous therapy cycle requires discontinuation, with the following exceptions:
 - Dosing delays to allow for prolonged steroid tapers to manage drug-related adverse events (allowed).
 - Dosing delays lasting >6 weeks from the previous dose that occur for non-drug-related reasons (may be allowed if approved by Study Conduct Group).
 - Prior to re-initiating treatment in a subject with a dosing delay lasting >6 weeks, Study Conduct Group must be consulted. Tumor assessments should continue as per protocol even if dosing is delayed. Periodic study visits to assess safety and laboratory studies should also continue every 6 weeks or more frequently if clinically indicated during such dosing delays.
- Any AE, laboratory abnormality, or intercurrent illness which, in the judgment of Clinical Investigator, presents a substantial clinical risk to the subject with continued nivolumab dosing.

For detailed information, please refer to the IB for nivolumab.

For FLOX, treatment will be permanently discontinued for the following reasons (in CTCAE grading):

- Grade 4 diarrhea (life-threatening consequences, urgent intervention indicated).
- Grade 3 sensory neuropathy (sensory alteration or paresthesia, severe symptoms, limiting self-care ADL).

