Appendix 6 – Management algorithms for adverse events caused by the Nordic FLOX regimen

The below criteria come to use each time a new series of FLOX cycles is commenced (irrespective of study treatment arm).

CTCAE grade	Description	Oxaliplatin	Fluorouracil
Diarrhea, grade 2	Increase of 4-6 stools per day over baseline; moderate increase in stoma output compared to baseline; not interfering with ADL	Interrupt until grade 1, then 100% dose first time, 75% dose second time, 50% dose third time	Interrupt until grade 1, then 100% dose first time, 75% dose second time, 50% dose third time
Diarrhea, grade 3	Increase of 7 or more stools per day over baseline; incontinence; severe increase in stoma output compared to baseline; interfering with ADL	Interrupt until grade 1, then 75% dose first time, 50% dose second time, discontinue third time	Interrupt until grade 1, then 75% dose first time, 50% dose second time, discontinue third time
Diarrhea, grade 4	Life-threatening consequences, urgent intervention indicated	Discontinue	Discontinue
Myelosuppression, grade 2	Neutrophils of 1.0 to less than 1.5, or platelets of 50 to less than 75	Interrupt until grade 1, then 100% dose first time, 75% dose and consider support with granulocyte-colony stimulating factor (e.g., pegfilgrastim) second or subsequent times	Interrupt until grade 1, then 100% dose first time, 75% dose and consider support with granulocyte-colony stimulating factor (e.g., pegfilgrastim) second or subsequent times
Myelosuppression, grade 3	Neutrophils of 0.5 to less than 1.0, or platelets of 25 to less than 50	Interrupt until grade 1, then 75% dose and consider support with granulocyte-colony stimulating factor (e.g., pegfilgrastim) first or subsequent times	Interrupt until grade 1, then 75% dose and consider support with granulocyte-colony stimulating factor (e.g., pegfilgrastim) first or subsequent times
Myelosuppression, grade 4	Neutrophils of less than 0.5, or platelets less than 25	Interrupt until grade 1, then 50% dose and consider support with granulocyte-colony stimulating factor (e.g., pegfilgrastim) first or subsequent times	Interrupt until grade 1, then 50% dose and consider support with granulocyte-colony stimulating factor (e.g., pegfilgrastim) first or subsequent times

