Sensory neuropathy, grade 2	Sensory alteration or paresthesia persisting between two oxaliplatin doses with no or only minor improvement, moderate symptoms, limiting instrumental ADL	Interrupt until grade 1, then 75% dose first time, 50% dose second time, discontinue third time	NA
Sensory neuropathy, grade 3	Sensory alteration or paresthesia, severe symptoms, limiting self-care ADL	Discontinue	NA

Units of measurement: neutrophils, $\times 10^9/L$; platelets, $\times 10^9/L$.

Abbreviations: ADL, activity of daily life; CTCAE, Common Terminology Criteria for Adverse Events; NA, not applicable.

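### For grade 3 sensory neuropathy, Protocol 5.7.2.3 read literally stops all of FLOX for good, while Appendix 6 stops oxaliplatin and marks fluorouracil as not applicable

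*Protocol*

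**What the plan says.** Section 5.4 of the Protocol defines FLOX as oxaliplatin on day 1 with bolus fluorouracil 500 mg/m² and folinic acid on days 1 and 2, every 2 weeks. Section 5.5 makes FLOX the whole of control-arm therapy.

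Section 5.7.2.3 introduces its chemotherapy stopping rules with "For FLOX, treatment will be permanently discontinued for the following reasons" and lists two events. The first is grade 4 diarrhea. The second is "Grade 3 sensory neuropathy (sensory alteration or paresthesia, severe symptoms, limiting self-care ADL". Neither is limited to one drug.

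Appendix 6 has one column for oxaliplatin and one for fluorouracil. The grade 3 neuropathy row, described as "Sensory alteration or paresthesia, severe symptoms, limiting self-care ADL", reads *Discontinue* for oxaliplatin and *NA* for fluorouracil. The table's footnote defines NA as not applicable. The grade 4 diarrhea row, described as "Life-threatening consequences, urgent intervention indicated", reads *Discontinue* in both columns.

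Sections 5.7.2 and 5.7.2.6 refer the reader to Appendix 6, the first for general guidelines and the second for more detail. The SAP does not deal with the point.

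**The concern.** Two operative instructions cover the same event and do not say the same thing about fluorouracil. One ends the whole regimen. The other ends oxaliplatin and prescribes no action for fluorouracil. Sites could treat identical patients differently while each follows the protocol.

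The consequence is plainest in the control arm. With FLOX permanently stopped, no study therapy is left and the patient moves to follow-up under section 7.7.3.2. On the Appendix 6 reading, the same patient could stay on study fluorouracil and folinic acid. Neuropathy is not a remote possibility, since section 5.4 lists it among the common toxicities of FLOX.

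**Working it through.** This is a comparison of texts, with one line of arithmetic at the end. The plan states no figure on this point to reproduce.

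**Step 1. Set the two events in the 5.7.2.3 FLOX list beside the table.**

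| Event | Section 5.7.2.3 | Appendix 6, oxaliplatin | Appendix 6, fluorouracil | Agree? |
|---|---|---|---|---|
| Grade 4 diarrhea | FLOX permanently stopped | Discontinue | Discontinue | Yes |
| Grade 3 sensory neuropathy | FLOX permanently stopped | Discontinue | NA | No |

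The table does write a full stop when a full stop is meant. Neuropathy is the only one of the two events where the texts part.

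**Step 2. Look for a text that settles it.**

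- Section 5.7.2.2 gives actions by drug for grade 2 neuropathy, but has no grade 3 neuropathy entry.
- Sections 5.7.2 and 5.7.2.6 point to Appendix 6 without ranking it against the body text.
- Appendix 6 says that its criteria apply whenever a new series of FLOX cycles starts, in either arm. It is therefore meant to be used, but this does not place it above 5.7.2.3.

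**Step 3. Look for the likely intent.**

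- At grade 2, section 5.7.2.2 and Appendix 6 both confine the action to oxaliplatin: interrupt, then 75%, then 50%, then discontinue at the third episode. The plan therefore already foresees a patient who has stopped oxaliplatin while fluorouracil is untouched.
- Together with step 1, this favours oxaliplatin only at grade 3. It remains an inference, because NA does not mean continue.

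**Step 4. Size of the difference.**

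Inputs, from section 5.4: fluorouracil 500 mg/m² per day on 2 days per cycle.

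Fluorouracil per FLOX cycle = 500 × 2 = 1000 mg/m².

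That is the study fluorouracil given under one reading and not under the other, for each remaining FLOX cycle. The documents give neither a rate of grade 3 neuropathy nor its timing, so no per-patient total and no number of patients can be derived.

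**The case against.** The strongest reply is that this is shorthand. Section 5.7.2.2 also uses FLOX as a label to separate chemotherapy from nivolumab, and an oxaliplatin-only bullet sits under that label. A clinician who turns to Appendix 6, as 5.7.2 directs, would probably stop oxaliplatin and think about fluorouracil separately. This stands as evidence of intent. It does not remove the mismatch, because 5.7.2.3 is a stopping rule in plain terms with no drug-level text beneath it for grade 3.

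A second reply is that NA is silence, so Appendix 6 never tells a site to keep giving fluorouracil. That is right, and the point should not be put more strongly. Even so, the site then has one text that stops the drug and a table that says no action applies to it.

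A reader might infer the same conflict at grade 2, because 5.7.2.1 states "FLOX administration will be delayed for the following reasons (in CTCAE grading" and lists "Grade 2 sensory neuropathy (sensory alteration or paresthesia persisting between two oxaliplatin doses with no or only minor improvement, moderate symptoms, limiting instrumental ADL". The documents do not support that. Section 5.7.2.1 lists triggers and sends the reader to 5.7.2.2 for resumption. There the general rule, "Subjects may resume treatment with study drug when the drug-related AE resolves to CTCAE grade ≤ 1 or baseline value", is followed by exceptions, and the oxaliplatin-only bullet for grade 2 neuropathy is one of them. Appendix 6 agrees. Nor can a grade 2 loss of fluorouracil be worked out from the limit "A treatment delay beyond 6 weeks is not allowed": under section 5.7.1, later doses follow the actual date of the previous cycle, so a delay moves the remaining cycles and does not in itself remove them.

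**Conclusion.** The grade 3 mismatch holds and is minor. Section 5.7.2.3 read literally stops fluorouracil and folinic acid along with oxaliplatin, Appendix 6 stops oxaliplatin and marks fluorouracil as not applicable, and nothing in the protocol decides between them. The difference is 1000 mg/m² of study fluorouracil per remaining FLOX cycle and, in the control arm, the end of all study therapy. That oxaliplatin only was intended is likely but not stated.

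A reader might infer that progression-free survival is affected, because section 5.5 ties failure of the strategy to progression on ongoing therapy. The documents do not support a claim of that kind. They give no neuropathy rate, the two texts apply in both arms, and section 7.6.5 keeps patients without progression under 8-weekly re-evaluation after protocol treatment stops. Fluorouracil outside the study is not barred either, since section 7.7.3.2 provides for recording new therapy. Whether oxaliplatin neuropathy also triggers the separate nivolumab stopping rules in 5.7.2.3 is another question, and nothing here rests on it.

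**What to change.** Make two edits, identical in both arms:

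1. Section 5.7.2.3, grade 3 neuropathy bullet: *Grade 3 sensory neuropathy: permanently discontinue oxaliplatin only; fluorouracil/folinic acid may continue at the same dose and schedule.*
2. Appendix 6, grade 3 neuropathy row, fluorouracil cell: replace *NA* with *Continue (with folinic acid)*.

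The direction is for the sponsor to confirm. If a full stop is intended, keep the 5.7.2.3 bullet and change that cell to *Discontinue*. Continuing folinic acid is inferred, because Appendix 6 has no column for it. Section 5.4 does not describe fluorouracil and folinic acid without oxaliplatin, which is why the new bullet states dose and schedule. The grade 2 text needs no change.

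The cost is a short amendment and a notice to sites. No extra patients, procedures or case report form fields are needed: section 5.2 already has each drug and dose logged, and section 9.3 already requires treatment changes in the medical record.

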5.7.2.4 Continuing nivolumab with suspected progression

Accumulating evidence indicates that a minority of subjects treated with immune-modulating therapy may derive clinical benefit despite initial evidence of disease progression, such as inflammatory reaction simulating progression, so-called pseudo-progression. Subjects may, at the discretion of Clinical Investigator, continue study treatment in the setting of suspected progression until progression is confirmed, in accordance with the evaluation algorithm detailed for RECIST/iRECIST (*c.f.*, [Paragraph 7.6](#)). If Clinical Investigator believes that the subject continues to derive clinical benefit by continuing treatment, the subject should continue monitoring/assessments according the same schedule as patients without tumor progression, with more frequent radiologic assessment if clinically indicated (see below).

Subjects may continue study treatment beyond initial (suspected) progression only if they meet the following criteria:

- Subject is in stable performance status (ECOG 0–1) and tolerates study treatment.
- Treatment will not delay intervention to prevent imminent complications.
- There is overall clinical benefit as judged by Clinical Investigator.

Radiographic assessment should be repeated after suspected progression as clinically required in order to determine whether there has been a decrease in the tumor size or continued progression. Potential for clinical benefit should be balanced by clinical judgment as to whether the subject is clinically deteriorating and unlikely to receive benefit from continued study treatment. Study treatment will be permanently discontinued upon confirmation of progression.

5.5.2.5 Management algorithms for immuno-oncology agents

These agents are associated with irAE that can differ in severity and duration from AE caused by other therapeutic classes. Nivolumab is considered an immuno-oncology agent in this protocol. Early recognition and management of irAE associated with immuno-oncology agents may mitigate severe toxicity. Management algorithms have been developed to assist investigators in assessing and managing the following groups of irAE:

- gastrointestinal
- renal
- pulmonary
- hepatic
- endocrinopathy
- skin
- neurological

Refer to [Appendix 5](#) for management details.

5.7.2.6 Management algorithms for the Nordic FLOX regimen

Refer to [Appendix 6](#) for further details.

5.7.2.7 Treatment of IMP-related infusion reactions

For **nivolumab infusion reactions**, the following information will be taken into consideration:

Since nivolumab contains only human immunoglobulin protein sequences, it is unlikely to be immunogenic and induce infusion or hypersensitivity reactions. However, if such a reaction were to occur, it might manifest with fever, chills, rigors, headache, rash, pruritus, arthralgias, hypotension, hypertension, bronchospasm, or other allergic-like reactions. Any CTCAE grade 3 or 4 infusion reaction will be reported within 24 hours as a serious adverse event (SAE) if it meets the criteria (*c.f.*, [Paragraph 8.1.2](#)). Infusion reactions will be graded according to the CTCAE v4.0 guidelines.

Treatment recommendations are provided below and may be modified based on local treatment standards and guidelines, as appropriate:

For grade 1 symptoms (mild reaction; infusion interruption not indicated; intervention not indicated):

- Remain with patient and monitor until recovery from symptoms. The following prophylactic premedications are recommended for future infusions: diphenhydramine 50 mg (or equivalent) and/or paracetamol (acetaminophen) 325 to 1000 mg at least 30 minutes before additional nivolumab administrations.

For grade 2 symptoms (moderate reaction requiring therapy or infusion interruption but responding promptly to symptomatic treatment, such as antihistamines, non-steroidal anti-inflammatory drugs, narcotics, corticosteroids, bronchodilators, IV fluids; prophylactic medications indicated for ≤ 24 hours):

- Stop the nivolumab infusion, begin IV infusion of normal saline, and treat the subject with diphenhydramine 50 mg IV (or equivalent) and/or paracetamol (acetaminophen) 325 to 1000 mg; remain with patient and monitor until resolution of symptoms. Corticosteroid and/or bronchodilator therapy may also be administered as appropriate. If the infusion is interrupted, restart the infusion at 50% of the original infusion rate when symptoms resolve; if no further complications ensue after 30 minutes, the rate may be increased to 100% of the original infusion rate. Monitor subject closely. If symptoms recur, no further nivolumab shall be administered at that visit.
- For future infusions, the following prophylactic premedications are recommended: diphenhydramine 50 mg (or equivalent) and/or paracetamol (acetaminophen) 325 to 1000 mg should be administered at least 30 minutes before nivolumab infusion. If necessary, corticosteroids (up to 25 mg of SoluCortef or equivalent) may be used.

For grade 3 or 4 symptoms (severe reaction; grade 3: prolonged, *i.e.*, not rapidly responsive to symptomatic medication and/or brief interruption of infusion; recurrence of symptoms following initial improvement; hospital admission indicated for other clinical sequelae, *e.g.*, renal impairment, pulmonary infiltrates); grade 4: life threatening; pressor or ventilatory support indicated):

- Immediately discontinue infusion of nivolumab. Begin IV infusion of normal saline and treat the subject as follows: recommend bronchodilators, epinephrine 0.2–1 mg of a 1:1000 solution for SC administration or 0.1–0.25 mg of a 1:10,000 solution injected slowly for IV administration, and/or diphenhydramine 50 mg IV with methylprednisolone 100 mg IV (or equivalent), as needed. Subject should be monitored until Clinical Investigator is comfortable that the symptoms will not recur. Nivolumab will be permanently discontinued. Clinical Investigators should follow their institutional guidelines for the treatment of anaphylaxis. Remain at bedside and monitor subject until recovery of the symptoms.

In case of late-occurring hypersensitivity symptoms (*e.g.*, appearance of a localized or generalized pruritus within 1 week after treatment), symptomatic treatment may be given (*e.g.*, oral antihistamine or corticosteroids).

For **FLOX infusion reactions**, management will be according to each participating department's SOP.

5.8 Concomitant treatments

It is expected that enrolled subjects will have systemic corticosteroids tapered as quickly as clinically appropriate during screening phase, and discontinued if possible prior to inclusion.

All concomitant medication (including over-the-counter drugs) used by the patient will be recorded.

Supportive care for all disease-related or treatment-related AE will be maximized for all subjects on this study.

5.8.1 Prohibited and/or restricted treatments

Immunosuppressive agents, including systemic corticosteroids, are prohibited during study treatment unless utilized to treat a drug-related AE. Subjects with a condition requiring systemic treatment with either corticosteroids (>20 mg daily prednisolone, >3 mg dexamethasone daily, or equivalent) or other immunosuppressive medications (including within 14 days of inclusion) are excluded. Subjects continuing to require supraphysiologic steroids (prednisolone >20 mg daily, >3 mg dexamethasone daily, or equivalent) may not be enrolled. Inhaled or topical steroids and adrenal replacement steroid doses (≤ 20 mg daily prednisolone daily, ≤ 3 mg dexamethasone daily, or equivalent) are permitted in the absence of active autoimmune disease.

Anticoagulant medication other than low molecular weight heparin is not permitted during active study treatment.

Brivudine, sorivudine, or analogs (antiviral drugs) are contraindicated during the use of fluoropyrimidine analogs and therefore not permitted during study treatment and the initial 4 weeks of planned treatment breaks.

